16.0 Online Data Collection

	We wil	ll not coll	ect data	through	an online	platform.
--	--------	-------------	----------	---------	-----------	-----------

- 1. List the online platform to be used. The preferred platforms are REDCap and Qualtrics, as these provide good data security and have options for collecting data without individually identifiable information.
 - All data will be collected using REDCap
- 2. If your intent is to collect the data without identifiers linked to an individual (including IP addresses), describe how you will ensure that no identifiable information will be associated with the data.

Qualtrics:	enable Anonymize Responses setting (removes IP	addresses and	f
location da	ta)		
REDCap:	use of the Public Survey Link		

- ☐ REDCap: use of a Participant List without a Participant Identifier field (Note: this does maintain a connection between the data and the individual, but it is only accessible to REDCap support personnel and not the researchers. Data collected in this manner should not be referred to as anonymous, but rather as data that is deidentified to the researchers).
- ☐ Other: Click here to enter text.

17.0 Data Analysis Plan

Directions: Describe the data analysis plan, including any statistical procedures. If applicable, provide a power analysis, and study/safety endpoints. Participant Demographic Characteristics Participant characteristics, including demographic and caregiving information (e.g., kin relationship) will be reported using frequencies, percentages, means, and standards of deviation. Comparison of Study and non-study participants.

Demographic characteristics of study and non-study participants collected from Eventbrite will be compared using t-test and chi-squared bivariate analyses, as well as frequencies and percentages. This will help the study team determine differences between caregivers who register for KINDER as a community program, and those who enroll in the study. Reasons for ineligibility and/or study or intervention withdrawal. The study team will also report the most frequent reasons for study or intervention withdrawal, as well as reasons participants were screened as ineligible, using frequencies and percentages. Outcomes. We will evaluate study outcomes using paired-t-tests comparing mean scores on all psychosocial outcomes collected before and after the intervention.

HRP- 503SBER	TEMPLATE: CWR	U SBER Protoc	ol
Approved:	09/2021	Prior Version:	05/2021

Satisfaction Surveys. To analyze items included in the satisfaction surveys, we will provide a percentage of each response for each item collected (e.g., 80% of caregivers "Agreed" or "Strongly Agreed" with this statement). A similar approach will be taken to evaluate reasons for non-participation. Fidelity Reports Fidelity reports will be evaluated using total scores averaged across all KINDER Discussion Sessions observed. We will be report these in aggregate and separated by facilitator and observer reports. We will divide reports by scores for adherence and quality. Scores will be reported using a percentage, as prior reports indicate 80% or more on fidelity scores indicates acceptable levels of fidelity. In addition—to examine variability in scores—we will also report this information using means and standards of deviation. Qualitative Interviews Qualitative interviews will be transcribed verbatim and identifying information removed. To conduct our thematic analysis, at least two members of the research team will read at least 2 transcripts and will decide on a preliminary codebook. The codebook will be applied to an interview and refined further prior to applying codes to the remaining interviews. At least two coders will analyze each transcript independently and will meet to compare codes and discuss differences in coding until agreements met. A second round of coding will be conducted to integrate new codes added during coding. Statistical Power and Same Size Our goal is to recruit at least N=46 of these caregivers into a research stι siz

18

udy to test preliminary efficacy. This N supports our ability to detect a small to moderate effecte.

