5.0 Number of Research Participants

Directions: Indicate the target number of research participants to be accrued locally, and, if this is a multi-site study, indicate the total number of research participants to be accrued across all sites.

Example language that can be used: We will enroll 25 subjects at CWRU and plan to enroll 150 subjects study wide. We will aim to enroll N=46 participants in order to achieve a sample

HRP- 503SBER	TEMPLATE: CWRU SBER Protocol		
Approved:	09/2021	Prior Version:	05/2021

size of N=34, which will enable us to detect a medium effect size using a single-sided paired t-test using an alpha of 0.05 at 0.80 power.

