Overall Study Design. We propose to conduct a single-arm pre- and post-test intervention study to evaluate the preliminary efficacy, as well as the acceptability and feasibility of the KINDER program. Participation includes completion of a 9-week intervention, as well as completion of two surveys (baseline and follow up). Total study participation is estimated to take 20 hours depending how long it takes caregivers to complete lessons and will be spread over 3 months. Intervention. KINDER is a 9 week digitally delivered psychoeducational intervention to promote healthy caregiving relationships by building caregiver resourcefulness, for the purpose of improving quality of care and preventing verbal elder mistreatment. Content includes a mix of synchronous and asynchronous activities, including three 1.5-hour group facilitated Discussion Sessions by Zoom, 3 check in calls with a facilitator of approximately 20 minutes each, and 8 independent lessons consisting of a story-based video, reading, reading quiz, reflection, and self-care goal. Lesson topics include understanding a dementia diagnosis, communicating with person you care for about challenging topics, finding a balance between safety concerns and independence, and more. Each lesson takes an estimated 1 hour to complete. Independent KINDER lessons can be completed using a printed or digital copy of the KINDER Workbook. Interventionist Training. Interventionists will undergo at least 2 hours of didactic training, in addition to selfstudy and shadowing or co-facilitating Discussion Sessions. Didactic training will include a review of the KINDER program and its underlying theory, review of the workbook and discussion sessions, and review of the facilitator guide. Didactic sessions will include active learning components, such as role-play of facilitator calls to participants. Before delivering sessions independently, facilitators will either shadow or co-facilitate KINDER sessions with another trained facilitator or the PI. Screening and Enrollment. Participants may complete eligibility online or by phone. If a participant completes the eligibility screening online and is eligible, they will receive a telephone follow up call from the study team member notifying them. (If the participant is not eligible following screening, they will receive an email notification.) During this call, the study team member will review the consent form with the participant and answer any questions they may have. If the caregiver would like to participate, they will be sent an email with a link to the consent form to complete. Interested caregivers who complete the eligibility screening by phone will undergo the same process, except the screening call will also include review of information in the consent form if the participant is eligible. **Recruitment.** Participants will primarily be recruited by contacting those caregivers who register to participate in KINDER on Eventbrite. Caregivers will be asked to indicate whether they would like to be contacted by researchers about a study on the KINDER program. The research team will then follow up to provide more information, altering between phone and email. (See Participant Communications.) Other methods of

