23.0 Withdrawal of Research Participants

Directions: Describe the anticipated circumstances under which research participants will be withdrawn from the research without their consent. Also include the procedures that will be followed when a research participant withdraws or are withdrawn from the research, including partial withdrawal from procedures with continued data collection. Participants may be withdrawn from the study if they 1) do not complete the baseline survey or 2) miss 2 or more group-based sessions. Participants may continue to participate in the KINDER program if this occurs but will be removed from the study. If this does occur, the PI will send an email to the participant to notify them. We will keep all data collected until withdrawal unless asked not to by a participant. We will attempt to contact participants to learn about their reason for withdrawal. See "Call Scripts for Caregivers Who Go Off Protocol"

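### The paired t-test leaves out the baseline scores of up to 12 caregivers the plan allows to lose; if loss is related to baseline score, the completers' change is a biased estimate for everyone with a baseline

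*Combined protocol and SAP*

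**What the plan says.** The design is single-arm with a baseline and a follow-up survey (Section 12.0). On sample size, Section 5.0 enrols 46 caregivers and gives the target for analysis as "size of N=34, which will enable us to detect a medium effect size". The calculation there rests on a one-sided 5% paired test with 80% power. The only outcome analysis, in Section 17.0, is: "We will evaluate study outcomes using paired-t-tests comparing mean scores on all psychosocial outcomes collected before and after the intervention".

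Section 23.0 sets out who may leave: "Participants may be withdrawn from the study if they 1) do not complete the baseline survey or 2) miss 2 or more group-based sessions". On their data it says: "We will keep all data collected until withdrawal unless asked not to by a participant".

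The plan names no analysis set, missing-data method or sensitivity analysis. Sections 12.0 and 28.0 monitor dropout and the proportion missing per variable every 3 months. Section 17.0 compares study with non-study caregivers on demographics and tabulates withdrawal reasons. It does not compare the baseline outcome scores of caregivers with and without follow-up.

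**The concern.** A caregiver with a baseline but no follow-up score contributes nothing to a paired t-test. If such caregivers start from different scores than those retained, the retained group's change will generally differ from that of the whole group, because the expected change depends on the starting score unless the follow-up-on-baseline slope is 1. Losing caregivers with better baseline scores overstates improvement. Losing those with worse scores understates it.

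With a single arm, no control group can offset this, so it passes directly into the preliminary-efficacy estimate of Aim 1, which is meant to inform later efficacy testing. The issue is separate from the attendance rule in Section 23.0: a caregiver who attends every session but never returns the follow-up survey is also dropped.

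**Working it through.** **The plan's own figures.** 46 − 34 = 12, and 12/46 = 26.1%. Working the other way, 34/(1 − 0.25) = 45.3, rounded up to 46. The plan therefore allows for about 25–26% loss, although it states no rate and no causes. Reading a medium effect as a standardised paired effect of 0.5 (an assumption), the exact non-central t calculation gives 27 pairs for the stated one-sided test (81.2% power), and 34 pairs give 88.7%. A two-sided test needs 34 (80.8%). So 34 fits a two-sided test rather than the stated one-sided one. That is a separate point, and what follows uses only the counts 46 and 34 and the one-sided 5% level.

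**Assumed inputs (none is in the documents).** Pre-post correlation ρ of 0.5 to 0.7; equal SDs at both waves, so that the slope b of follow-up on baseline equals ρ; a baseline gap g between lost and retained caregivers of 0.45 to 0.8 SD.

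**Bias of the completers' mean change.** Let k be the number of lost caregivers who have a baseline score. Relative to all 34 + k caregivers with a baseline:

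- size of bias in baseline SDs = (1 − b) × k/(34 + k) × g
- SD of change = √(2(1 − ρ))
- size of bias in SDs of change = √((1 − ρ)/2) × k/(34 + k) × g

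With k = 12, k/(34 + k) = 0.261:

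| ρ | g | Bias (SD of change) |
|---|---|---|
| 0.5 | 0.45 | 0.500 × 0.261 × 0.45 = 0.059 |
| 0.5 | 0.80 | 0.500 × 0.261 × 0.80 = 0.104 |
| 0.7 | 0.45 | 0.387 × 0.261 × 0.45 = 0.045 |
| 0.7 | 0.80 | 0.387 × 0.261 × 0.80 = 0.081 |

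If only 4 of the 12 have a baseline, k/(34 + k) = 4/38 = 0.105, and the range falls to 0.018 (0.387 × 0.105 × 0.45) to 0.042 (0.500 × 0.105 × 0.80).

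**Effect on the one-sided 5% test (k = 12).** With no true change, a non-central t with 33 df and non-centrality bias × √34 rejects 8.3% of the time at a bias of 0.045 and 14.7% at 0.104. Simulations of 46 caregivers with loss depending on baseline gave 7.9% (ρ 0.7) and 10.3% (ρ 0.5) at gaps of about 0.48, and 12.3% and 15.2% at gaps of about 0.85. A second set, with exactly 12 lost and gaps of 0.45 to 0.82, gave 8.6% to 15.8%. In the opposite direction, power at a true effect of 0.435 (80% with 34 pairs) falls to 72% at a bias of 0.045 and 60% at 0.104.

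**What a two-wave likelihood model does.** With unstructured covariance the estimate is:

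completers' mean change + (b − 1) × (baseline mean of all − baseline mean of completers)

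- Loss depending on baseline: simulated bias was within 0.004 SD of change. At ρ 0.5 and a gap of about 0.48, type I error was 5.1%, against 10.3% for the paired t-test.
- Loss depending on the unobserved change: most of the bias stays, falling only from 0.125 to 0.095 (ρ 0.5) and from 0.126 to 0.108 (ρ 0.7). At ρ 0.5 the model's type I error is 13.4%, against 17.8%.
- Precision: the large-sample variance ratio is [(1 − ρ²)/34 + (1 − ρ)²/(34 + k)] ÷ [2(1 − ρ)/34]. With k = 12 it is 0.935 (ρ 0.5) and 0.961 (ρ 0.7); with k = 4 and ρ 0.5 it is 0.974. At a gap of about 0.85 the simulated SD was slightly worse than for pairs (0.174 against 0.171).

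**Why the covariance matters.** A random-intercept model forces equal variances at the two waves. In 400 simulated studies (ρ 0.6, gap about 0.95 SD, no true change, units of baseline SD), a follow-up SD of 0.7 times baseline gave a bias of 0.151 for pairs and 0.054 for the random-intercept model. At 1.3 times baseline, the figures were 0.060 and −0.054. An unstructured estimate was near zero in each.

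**Zero-change scenario.** If no lost caregiver changed, the effect among all with a baseline is 34/(34 + k) of the completers' effect: 34/46 = 74% for k = 12, or 34/38 = 89% for k = 4.

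**The case against.** A reader might infer that 12 baseline scores are thrown away. The documents do not support that count. Failing to complete the baseline survey is itself a ground for withdrawal in Section 23.0, and a withdrawn participant may ask that data not be kept. Twelve is an upper limit.

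A reader might also infer that a mixed model recovers the lost information free of charge. It does not. It assumes that loss is explained by observed baseline scores, whereas missing sessions may reflect how the caregiver is responding. It also changes the target. The hypothesis in Section 2.0 concerns improvement following participation, and for caregivers who participated and were followed up the paired t-test is not biased by this mechanism.

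Nor do the documents show that the result will be biased, or in which direction. The correlation and gap are assumptions, and the bias is zero if there is no gap or the slope is 1. Baseline scores are not wholly unused either, since the quarterly reports describe study variables. Reminders (Section 12.0) and payment of $75 per survey (Section 26.0) should limit loss, and this is a pilot.

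All of this stands. It narrows the claim but leaves the gap: the plan does not say whom the estimated change describes, and it offers no check on whether lost and retained caregivers differ at baseline.

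**Conclusion.** The concern holds in a conditional form. The outcome analysis excludes available baseline scores from up to 12 of 46 caregivers. If loss is related to baseline score and the slope is not 1, the completers' mean change is biased for all caregivers with a baseline. With all 12 baselines on file and the assumed correlations and gaps, the bias is roughly 0.05 to 0.10 SD of change in either direction, and one-sided type I error reaches about 8% to 16% in the adverse direction. With fewer baselines on file both are smaller.

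This is modest, but not trivial beside the 0.435 SD that 34 pairs can detect with 80% power. The case for change rests on bias and transparency, not on precision.

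**What to change.** In Section 17.0:

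1. State that the target is all enrolled caregivers with a baseline score.
2. Estimate the pre-post change for each outcome with a two-wave repeated-measures likelihood model with unstructured covariance, REML and a small-sample degrees-of-freedom correction. Do not use a random intercept with equal variances.
3. Keep the paired t-test as the complete-pair result.
4. Compare baseline outcome scores of caregivers with and without follow-up.
5. Add a sensitivity result that sets missing changes to zero.

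The cost is SAP wording and a few lines of code; no new data or participants are needed. The downsides are that most of the bias remains if loss depends on the unobserved change, that the precision gain is negligible, and that precision can be slightly worse when the baseline gap is large. Items 4 and 5 let readers judge how far the main estimate depends on its assumption.

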2.0 Objectives

Directions: Describe the purpose, specific aims or objectives. Be sure to also include the hypothesis being tested. Aim 1: Test the preliminary efficacy of KINDER. The investigators hypothesize caregivers will report improved resourcefulness (mediator for future study) and relationship quality (primary outcome) following participation. Further, caregivers will report higher quality of care and reduced frequency of verbal mistreatment (distal outcomes). **Aim 2:** Determine acceptability among caregivers and feasibility with satisfaction surveys and fidelity reports.

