3.0 Background

Directions: Describe the relevant prior experience and gaps in current knowledge describing how this study will add to existing knowledge. Include any relevant preliminary data. What is KINDER? KINDER is a psychoeducational intervention to prevent and mitigate the occurrence of verbal-type elder mistreatment by family caregivers to persons living with dementia. Content focuses on building healthy and respectful caregiving relationships (Benton & Meyer, 2022). KINDER focuses on verbal mistreatment among families living with dementia, since it is estimated that one- to two-thirds of family caregivers engage in potential mistreatment, of which verbal mistreatment is the most common type (Cooper et al., 2009; Orfila et al., 2018; Pickering et al., 2019; Wiglesworth et al., 2010). Beyond verbal mistreatment, KINDER also seeks to promote high-quality care by family members, including provision of care that is respectful (Christie et al., 2009; Dooley et al., 2007). KINDER was developed by [name], at Case Western Reserve University's Frances Payne Bolton School of Nursing and

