4.0 Inclusion and Exclusion Criteria

Directions: Describe how individuals will be screened for eligibility.

Participants may complete eligibility screening by phone or begin the screening online. Participants who complete screening online will receive a telephone follow up to complete any questions they may have missed and answer questions they may have.

Using the tables below, describe the inclusion and exclusion criteria that will define who will be included and excluded in your final study sample.

	Inclusion		
1.	Is age 18+		
2.	Provides care to a family member or friend living with Alzheimer's Disease or a		
	related dementia. This does not have to be diagnosed.		
3.	Participant helps with at least 1 activity of daily living (e.g., bathing) or 2 instrumental		
	activities of daily living (e.g., shopping)		
4.	Participant provides at least 8 hours of assistance to the care recipient per week		
5.	Participant does not intend to place the care recipient in a skilled nursing facility		
	within 3 months of consenting into the study		

		Exclusion
	1.	Does not read and speak English
ſ	2.	Does not have reliable access a computer and internet

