2. List all other data to be collected for the research study. Attach all data collection tools on the Local Site Documents page of the SpartaIRB smart form (Other Attachments). **Eventbrite Registration:** Name, email, phone number, mailing address, year born, gender, race, ethnicity, education, financial strain. (Participants are notified that demographic information is optional to provide and will be used by the study team.) **Screening:** Year born, caregiving status, hours of caregiving, access to technology, care recipient functional ability, plans for nursing home placement, name, email, phone number. Interested participants are notified that they may also provide demographic information to help the study team understand differences between those eligible and ineligible for participation. These items are consistent with those required by the NIA CROMS data collection items: biological sex, gender identity, sexual orientation, race, ethnicity, highest level of education, marital status, financial strain, kin relationship to care recipient, primary language. Off-Study Reason. Reason for withdrawing from study; reason for ending intervention participation **Baseline Demographic Information**: Year born, gender identify, race, ethnicity, marital status, education, current employment, financial strain, kin relationship to care recipient, primary care status, living situation

HRP- 503SBER	TEMPLATE: CWRU SBER Protocol		
Approved:	09/2021	Prior Version:	05/2021

with care recipient, length of care, weekly hours of care. **Baseline and Follow Up Survey Measures:** Revised Memory and Behavior Checklist, Dyadic Relationship Scale, Depressive Cognitions Scale, Relational Certainty, Resourcefulness, Caregiver Self-Efficacy Scale-8, Modified Conflict Tactics Scale, Task Management Scale Index, Exemplary Care Scale. **Satisfaction:** Satisfaction with the KINDER program and components **Reason for non-participation.** Reason the registered individual did not attend KINDER or attended <2 sessions. **Facilitator Call Log:** Completion of facilitator calls with participants **Facilitator Fidelity Form:** Name of facilitator and session date, perception of sessions (e.g., participant engagement, adherence to session agenda), participant attendance

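### Is the paired t-test the wrong planned test for verbal mistreatment frequency, where many caregivers may score zero?

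*Combined protocol and SAP*

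**What the plan says.** Section 17.0 (Outcomes) gives one method for the survey outcomes: they are evaluated "using paired-t-tests comparing mean scores on all psychosocial outcomes collected before and after the intervention". It names no rank test, transformation or fallback, and it does not state sidedness. Section 5.0 sizes the study at 34 analysed caregivers (46 enrolled) "using a single-sided paired t-test using an alpha of 0.05 at 0.80 power".

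Section 2.0 names "relationship quality (primary outcome" and then, further down the causal chain, "reduced frequency of verbal mistreatment (distal outcomes". Section 15.0 lists the survey measures taken at baseline and follow-up, among them "Modified Conflict Tactics Scale, Task Management Scale Index, Exemplary Care Scale". The first of these is presumably the mistreatment measure, but the documents do not make that link and give no scoring or range.

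On how common the behaviour is, Section 3.0 says "it is estimated that one- to two-thirds of family caregivers engage in potential mistreatment". Section 4.0 selects on age, caregiving role, tasks, hours ("Participant provides at least 8 hours of assistance to the care recipient per week") and placement plans, and not on mistreatment.

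**The concern.** If one- to two-thirds of caregivers engage in potential mistreatment and nobody is screened in for it, one- to two-thirds may score zero or close to it at baseline. Many would then have no room to improve, and the mean change would come from a minority with skewed scores. A t-test on such data may lose power, and a few high scorers can weigh heavily on the mean. The behaviour concerned is the one KINDER is meant to prevent, and Section 3.0 says the findings will inform later efficacy testing. A rank test for this one outcome would cost a sentence or two, and naming it in advance would avoid a choice made after seeing the data.

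**Working it through.** **The plan's own figure.** With a paired d of 0.5 assumed for a medium effect, the noncentral t distribution (33 df) gives power 0.808 at n = 34 for a two-sided 0.05 test and 0.887 for a one-sided one. A one-sided test would need 27 pairs. So 34 is reproduced under the two-sided reading. That mismatch with Section 5.0 is a separate matter. Here it matters only that N was not derived from the mistreatment score.

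**Possible floor.** 34 × (1 − 2/3) = 11.3 and 34 × (1 − 1/3) = 22.7, so about 11 to 23 of 34 caregivers, if the prevalence in Section 3.0 applies to this sample and means any non-zero score. The documents establish neither.

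**Power and error rate.** The score distribution is not given, so it is assumed:
- Each caregiver has a gamma-distributed rate (mean 4 or 8, shape 0.5 or 1), with Poisson counts before and after and a rate cut by 40%.
- Never-engagers are added to bring baseline zeros to one-third or two-thirds. One noisy scenario (mean 4, shape 0.5) could not go below 44%.
- Noise, where used, is an independent factor per visit with mean 1 and coefficient of variation 1.
- The test is one-sided at 0.05. The Wilcoxon test drops zero changes and uses the tie-corrected normal approximation.

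Power without a maximum score, t-test / Wilcoxon:

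| Scenario | mean 4, shape 0.5 | mean 4, shape 1 | mean 8, shape 0.5 | mean 8, shape 1 |
|---|---|---|---|---|
| Steady rate, 1/3 zeros | 0.948 / 0.934 | 0.933 / 0.920 | 0.990 / 0.986 | 0.988 / 0.983 |
| Steady rate, 2/3 zeros | 0.672 / 0.691 | 0.651 / 0.662 | 0.802 / 0.832 | 0.804 / 0.817 |
| Noisy, 1/3 zeros | 0.313 / 0.367 | 0.392 / 0.425 | 0.321 / 0.396 | 0.378 / 0.416 |
| Noisy, 2/3 zeros | 0.199 / 0.255 | 0.225 / 0.259 | 0.170 / 0.241 | 0.210 / 0.268 |

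- With a steady rate and one-third zeros, the Wilcoxon test is lower in all four columns (for example 0.934 − 0.948 = −0.014). With two-thirds zeros it gains 1 to 3 points. Gains above that appear only in the noisy rows.
- With a maximum score, which is the more natural reading of a survey scale, the difference is about −1.7 to +0.8 points (maximum 12) and −1.6 to +2.2 points (maximum 20).
- With Pratt's handling of zero changes, power can be up to about 9 points below the t-test. It gains, by about 1 to 6 points, only without a maximum and with noise.
- With no true change, the one-sided error rate is 4.0 to 5.6% for the t-test and 4.7 to 5.7% for the Wilcoxon test.
- The floor matters far more than the test. Going from one-third to two-thirds zeros at a steady rate costs the t-test 18 points (0.988 − 0.804) to 28 points (0.933 − 0.651), and most of that loss remains under either test.

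**Could one or two caregivers carry a positive result?** In these simulations the two largest changes supply a median 48 to 82% of the sum of squared changes (33 to 64% with a maximum of 12). That share measures their contribution to the variance, so it inflates the denominator of t as well as moving the mean. Suppose k of n caregivers change by the same amount and the rest do not change. Then

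t = √[k(n − 1)/(n − k)].

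For n = 34:
- k = 1: √(33/33) = 1.00
- k = 2: √(66/32) = 1.44
- k = 3: √(99/31) = 1.79

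The one-sided critical value is 1.69. One or two caregivers alone cannot reach it, but three equal changes can. The Wilcoxon test is no sturdier here. With three equal changes and zeros dropped, each rank is 2, the rank sum is 6 against an expected 3, and the tie-corrected variance is 3 × 4 × 7/24 − (27 − 3)/48 = 3. So z = 3/√3 = 1.73 and p = 0.042, whereas the exact p is (1/2)³ = 0.125.

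**The case for a change.** The best case for a rank test is that the floor can be foreseen from the plan's own background, and that in some plausible models the gain is not trivial. With the frequency halved instead of cut by 40%, two-thirds of caregivers always at zero and no maximum, one-sided power rises from 0.390 to 0.501 in the most skewed case, a gain of 11 points. With a maximum of 20 it rises from 0.445 to 0.485 or 0.491, a gain of 4 to 5 points. Tested two-sided, the gain reaches 17 points without a maximum and about 9 points with a maximum of 20. Section 17.0 does not state sidedness.

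These figures stand, but they are conditional. In the halved-frequency model, two-thirds always at zero means about 75 to 77% zeros at baseline, beyond the range in Section 3.0, and power stays at or below about 0.50 under either test. With one-third always at zero and a maximum of 20, the one-sided results are level (0.790 against 0.791, and 0.760 against 0.765). The large two-sided gains depart from the one-sided test that Section 5.0 names. The t-test falls behind there because it is conservative, so it does not produce false positives.

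It is also true that fixing a test in advance is better than switching after seeing skewed data. But the plan has fixed one. A few extreme scores can sway the estimated mean change, and a different test leaves that estimate as it is.

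**Conclusion.** The concern does not hold. The planned paired t-test is valid for this outcome and directly tests a change in mean frequency, which is what Section 2.0 hypothesises. The signed-rank test concerns the distribution of the paired differences. Whether it has more power depends on three things the documents do not settle: whether the score has a maximum, how variable it is from visit to visit, and how zero changes are treated. For a bounded score and a 40% reduction, the one-sided difference is about two points or less either way. With Pratt's zero handling the change can lose up to about 9 points.

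The conclusion assumes 34 analysed pairs, the one-sided 0.05 test of Section 5.0 and the distributions set out above. The scoring would be in the data collection tools, which Section 15.0 places in separate attachments. An unbounded, very skewed score with more than two-thirds zeros would favour the rank test, but both tests would then be well short of 0.80 power. Given a distal outcome in a pilot, with the primary outcome and N untouched, this is a choice on which statisticians may reasonably differ. Reporting the share at zero before and after would be useful description, but its absence is not a fault in the plan.
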